### **C.2.b Adaptation to Include Tailoring to Parents (White, Black, and Hispanic)**

Similarly to C.2.a, focus groups will be conducted to garner parent input to ensure the messages are relevant.

**Population and Recruitment** – A convenience sample of parents (6 to 8 for each of 6 groups) will be recruited via flyers distributed in health care settings, community agencies, and places of worship with a number to text/call if interested. The project manager will contact parents to describe the project and schedule them for a focus group. Two focus groups will be conducted for each race/ethnic group in the project. For Hispanic parents one will be conducted in English and 1 in Spanish. Additional groups will be conducted if needed to achieve thematic saturation. Consent will be obtained at the focus group. A \$25 incentive will be given.

**Focus Groups** – The same format will be followed as described above to assess, revise and test the messages.

### **C.2.c Expansion of Tailored Menu Recommendations**

Menus will be obtained from restaurants suggested by participants that are not included in the current data base. The healthiest options will be identified from each venue for a variety of categories (e.g., salty foods, dairy foods, etc). The current lists will be augmented with these options and used to offer suggestions based on users' location and preferences (e.g., in McDonald's a participant who said they like dairy foods on the baseline survey, might be asked to try a parfait). In addition, menus from the top 300 restaurant franchises in the US will be added. Thus, tailored suggestions will be available for the vast majority of places where participants eat.

**Outcomes:** At the completion of Aim 1 and 2 activities, the enhanced LIITAH system will be relevant to a wider range of users, it will allow parents (and friends if desired) to participate and will have additional engagement features. This enhanced system will be integrated into the Fruit Street platform and will be ready to be tested to demonstrate its impact.

## **C.3. Trial (Aim 3)**

**Rationale:** We will demonstrate the impact of using LIITAH on decreasing calories purchased from restaurants by adolescents, along with the number of visits to restaurants and the impact on their BMI.

**Overview:** The trial will consist of 2 arms (an intervention and a control arm) over the course of 3 months.

**Intervention Group** – Will receive the full version of the LIITAH app which consists of 5 components that allow 1) Enhanced Location Identification (ELI), 2) Self-report of Nutrients by Annotated Photos (SNAP), 3) delivery of individually and culturally tailored point of purchase (POP) prompts along with tailored messages sent at other times of day (determined by the participant), 4) use of the app in connection with parents, 5) goal setting capacity, and 6) a point system.

**Control Group** – Will receive a version of the app with only the ELI and SNAP components. Thus, it will detect their presence in a restaurant and allow users to document their purchases by submitting annotated photos, but it will not deliver any POP prompts encouraging them to make healthy choices, or messages at other times of day. It will not allow goal setting or assign points. The control parents will receive a version of the app with only the ELI system to detect when they are in an eating venue and the SNAP component so they can submit and annotated photo of any food they purchase from a restaurant for their adolescent.

**Primary Outcome** – Data regarding the number of calories purchased will be calculated based on the photos submitted and the calorie content as listed in the nutrition information from the restaurant. Comparisons will be made between groups to determine the impact of the program on calories purchased. In addition, 24-hour food recalls will be conducted in the baseline week and final week (3 per week) to provide a comparison assessment of caloric intake from restaurants and to explore changes in caloric intake overall.

While photo documentation decreases cost, compared to 24-hour food recalls, it may have an intervention effect. The possibility exists for the Hawthorne effect (i.e., recording may alter behavior) to cause a decrease in the calories purchased by the control group. However, we anticipate that this will be negligible as adolescents take pictures (e.g., Instagram, snapchat) of things like their food frequently, making it unlikely that the control group will be significantly impacted by submitting pictures of their food purchases.

**Secondary Outcome A** – The number of times the app identifies that users are in a restaurant will be recorded automatically and compared between groups to reveal the program's impact on restaurant visits.

**Secondary Outcome B** – Height and Weight will be obtained at enrollment and post-intervention sessions to determine potential changes in BMI. Though it is likely that use over a longer time will be needed to achieve a statistically significant decrease in BMI, these measures will be obtained to determine if a trend towards a decreased BMI will be demonstrated by the intervention group.

**C.3.a. Population and Recruitment.** We will recruit a total of 150 adolescent/parent dyads from schools, hospitals and places of worship using the methods described above, to participate in the trial, with the goal of recruiting approximately one third of the participants from each of the 3 ethnic groups targeted for this trial. In addition, within each ethnic group we will recruit adolescents in the normal weight, overweight and obese categories (a third each). Recruiting 150 dyads will allow for an expected attrition rate of 20% and still provide the 120 dyads needed to have the power to detect the anticipated changes. Inclusion Criteria: Adolescents 13 – 17 years of age, who eat restaurant food at least 3 times per week, and have a parent who agrees to participate. The RA will contact those who text/call indicating an interest in participation. During the call a baseline enrollment session will be scheduled. Dyads will receive a \$50 gift card at baseline as an incentive for participation and an additional \$50 for each of the two follow-up assessments. A cell phone and payment for data plans will be provided for those who need these in order to participate.

**C.3.b. Enrollment Session.** Consent/assent will be obtained and height and weight will be measured for adolescents and their participating parents. They will individually complete an online enrollment survey addressing demographics, baseline characteristics, preferences, their level of interest in making dietary changes and any specific changes they wish to make. Adolescent/Parent dyads will download [the LIITAH app](#) and receive instruction in its use and ways to tailor features to their preferences (e.g., graphics, language).

Ame00105576 The focus group part of the study has been completed for both parents and all teens on 9/2020. Due to the COVID-19 situation that hampers physical contact, recruitment for the research study trial (to replace the in-person enrollment sessions due to the COVID situation) will be conducted virtually through UMHealthResearch.org and through a Facebook and Instagram advertising campaign managed by MICHR and linked to our UMHealthResearch study page.

**Randomization:** The technology team will randomly assign dyads as they enroll to either the intervention the control group. They will then adjust the functionality of the app for the participants accordingly, and will send a message to their phone indicating their group assignment, along with instructions for their group.

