**Dyad Component** – Parents will download a parent version of the app that will allow them to see their child's goals and negotiate rewards (as noted above). They will be able to send “high fives” to their adolescent for making good choices. They will also receive a message when they enter an eating venue that asks if they plan to purchase food for their adolescent. If yes, then they will receive a suggested healthy item that their adolescent might like (based on the adolescent's data). The child will be notified that their parent has responded in the app and they can send a message (e.g., they do not need fast food, asking for a specific option, or suggesting another venue). If both parents have enrolled, then the other parent would also get these messages. Depending on user interest, a version of the dyad component may be created for friends.

**Scaling** – The phase 1 project was a proof of concept that included only 30 restaurants and the program was tested with a small number of adolescents. During phase 2 we will increase this to include the 300 largest franchises in the US and testing with Fruit Street will determine what is required for scale up to include venues number greater than 1000. Our PiLR mBaaS is a multi-tenant system that runs on the Amazon Web and MongoDB cloud services. This configuration minimizes cost and IT management. During Phase 1, the PiLR architecture supported 100 participants per project and up to 2,000 in aggregate. Since then, PiLR has been reconfigured for 10 times greater capacity. It currently supports projects of 3,000 participants and is capable of up to 10,000 per project. This is sufficient for the proposed project. However, commercialization by Fruit Street will require up to another 10 fold increase in capacity. As part of this project, MEI and Fruit Street developers will review the architectures of both systems to evaluate the most appropriate means of integration.

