### **C.3.c. Six-Week Intervention**

**Baseline Data:** For the first 2 weeks the app will only record presence in a restaurant and ask users to submit photos of their food. In week 3 the program features will be activated for the intervention group.

**Intervention Group:** *Point of Purchase (POP) messages will encourage healthy choices when participants are noted to be in a restaurant.* Participants will be asked to keep the app running on their phone. They will receive a ping when the app identifies that they are in a fast food restaurant followed by a POP prompt, tailored to their preferences and the options available at that location. If they are in a venue without a menu (though this is unlikely as most participants in the developmental project frequented popular franchises with published menus), general healthy suggestions will be provided (such as “consider choosing smaller portions” or “does this venue sell fruit?”). If the app does not ping when they enter a restaurant, they will be asked to register that location by tapping the ‘register location’ button on the app and entering the restaurant name. For detection errors, the appropriate stored venue criteria (location, geo-fence, time of day or dwell time) may be adjusted to improve detection. Users will also be asked to take a picture of any items they buy and to annotate it with information that would help to determine the nutrients in the food. Annotations may be audio, text, or made from a selection of descriptive buttons (e.g., to indicate small, medium or large sizes).

Tailored healthy lifestyle messages will be delivered at times selected by participants. In addition to messages prompting healthy choices at the point of sale, participants will receive tailored messages promoting healthy lifestyle choices. Participants will select the timeframe during which they would like to receive these daily messages. The messages will be tailored to their values, characteristics and preferences, and will address topics such as increased physical activity, obtaining sufficient sleep, and healthy nutrition. As described above, these messages will be based on Self Determination Theory and use motivational interviewing approaches.

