#### **C.3.e. Analyses**

Primary Outcome – Calories purchased (by and for adolescents) will be assessed using annotated photos, and nutrition data from restaurant menus (e.g., if the participant submits a picture of McDonald’s fries and indicates that it is a small order, then from the McDonalds menu, we will determine that the calories purchased were 240 kcals). Number of visits will be obtained from the app. We will use population averaged generalized estimating equation regressions (GEE) to compare trajectories of calories purchased and number of visits between groups. The GEE approach allows us to account for the correlation in repeated observations collected from subjects over time. For calories purchased, we will perform GEE linear regression modeling as a function of time, treatment group (intervention vs. control) and the interaction of time by treatment group ( $Y = \beta_0 + \beta_1 Time + \beta_2 Treatment + \beta_3 Time * Treatment + \epsilon$ ). Residual diagnostics will be performed to examine departures from model assumptions. If needed, we will use transformed outcome variables and refit the models.

Secondary Analyses – Similarly, for the number of visits by the adolescents to restaurants, we will fit a GEE Poisson regression model as a function of time, treatment group (intervention vs. control group) and the interaction of time by treatment group. For change in BMI, we will perform multiple linear regression of change as function of initial BMI and treatment group. We will add participant characteristics to the models discussed above and explore associations between the outcomes and covariates of interest (e.g. extent of app use, initial BMI (adolescent and parent), race/ethnicity). In additional exploratory analyses, using methods described above, changes in calories purchased from restaurants as assessed by the 24-hour recalls will also be examined to compare findings with the photo documentation method of assessing calories. Pre-post changes in total calories reported via the 24-hour food recalls will also be calculated and compared between groups.

Power – The trial will be powered on average calories purchased in restaurants. The average child consumes 765 calories per meal eaten away from the home and the average child eats 2.5 meals per week away from the home. While the trial population eat out more often at baseline, this conservative estimate was used in the

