power calculation. Programs for youth suggest benefits from a 250 kcal deficit per day. We determined that a clinically significant change would be a minimum decrease of 650 kcal/week. A sample size of 60 in each group (intervention vs. control group) will have 80% power to detect a difference of 650 kcal/week using a two group t-test with a two tailed alpha of 0.05 and a standard deviation of 1200 kcals. Thus by recruiting 75 adolescents per group even with a 20% attrition we will have the power to detect the expected results.

**Qualitative Analysis** –From the post-trial interviews and the satisfaction survey we will identify participants' perceptions of the intervention overall and of the messages specifically, using the qualitative methods described above. We will explore potential differences for parents' vs adolescents' and by race/ethnicity.

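### Parent-bought food counts in the primary outcome, but parents are prompted differently by arm from week 3 and no rule says whose photo counts

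*Combined protocol and SAP*

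**What the plan says.** Section C.3.e defines the primary outcome to include parents' purchases: "Calories purchased (by and for adolescents) will be assessed using annotated photos". Two phones per dyad therefore feed one endpoint. Aim 3 and the C.3 rationale speak only of purchases by adolescents.

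The parent apps are described in two places:

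- **Control (C.3, Control Group).** Parents get restaurant detection (ELI) and "the SNAP component so they can submit and annotated photo of any food they purchase from a restaurant for their adolescent". Nothing else is provided.
- **Intervention (C.1, Dyad Component).** Parents can see goals, negotiate rewards and send encouragement. "They will also receive a message when they enter an eating venue that asks if they plan to purchase food for their adolescent". If the answer is yes, the app suggests an item, and the adolescent is told that the parent has responded. This paragraph does not mention a parent photo. C.3 lists SNAP among the components of the full app given to the intervention group, without saying whether the parent's version has it.

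On timing, C.3.c states: "For the first 2 weeks the app will only record presence in a restaurant and ask users to submit photos of their food". Intervention features are activated in week 3. No section says which record counts if parent and adolescent both photograph one meal, or what happens when a parent's purchase has no photo.

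**The concern.** An outcome built from user-submitted photos is only as comparable between arms as the process that brings the photos in. Here one source of those photos, the parent, is reminded about buying for the adolescent in one arm through a question that the other arm's app is not described as asking. The reminder could raise recording in the intervention arm. It could also lower it, if answering the question feels like having reported the meal. Either way, a difference in recorded calories could reflect capture and not purchasing.

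The channel is not negligible. Section B.1 says that parents often buy the family's restaurant food, and the Phase 1 pilot results report that parents frequently do so when the adolescent is not there. In that situation the parent's photo may be the only record made at the point of purchase.

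The common two-week baseline does not protect the comparison. A capture difference that begins in week 3 is a between-arm difference in change over time, which is what the time-by-treatment term in C.3.e estimates.

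**Working it through.** **Inputs (C.3.e, except where noted)**
- 765 kcal per meal away from home; 2.5 such meals per week as the planning value. Inclusion minimum: 3 restaurant meals per week (C.3.a).
- Target and power: the plan says its sample "will have 80% power to detect a difference of 650 kcal/week". The calculation behind this is an unpaired t-test at the two-sided 5% level, with SD 1200 kcal and 60 analysed per group.
- q, the net between-arm difference in recorded parent-bought meals per dyad per week. The documents do not give it, so it is an assumption shown over a range.

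**Step 1: the plan's own figure.** With a difference of 650, SD 1200 and two-sided alpha 0.05, 80% power needs 54 per group (normal approximation) or 55 (t-test). At 60 per group power is 84.3% or 83.7%. The stated 60 is not reproduced exactly, but it errs on the conservative side and does not affect this point. The attrition step reproduces: 60/(1 − 0.20) = 75 per group.

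**Step 2: size of the shift.** Shift = q × 765 kcal/week, compared with 650.
- q = 0.10: 76.5 kcal/week; 76.5/650 = 12%
- q = 0.25: 191 kcal/week; 191/650 = 29%
- q = 0.50: 382.5 kcal/week; 382.5/650 = 59%
- Break-even: 650/765 = 0.85 meals/week, which is 0.85/2.5 = 34% of the planning value or 0.85/3 = 28% of the inclusion minimum.

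**Step 3: effect on inference.** Standard error = 1200 × √(2/60) = 219 kcal/week; noncentral t with 118 df. This uses the t-test of the power calculation as a stand-in for the GEE model, so the figures are illustrative.

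| q (assumed) | Shift, kcal/week | Chance of p<0.05 with no true effect | Power for a true 650 reduction if the shift opposes it |
|---|---|---|---|
| 0 | 0 | 5% | 84% |
| 0.10 | 77 | 6% | 74% |
| 0.25 | 191 | 14% | 55% |
| 0.50 | 383 | 41% | 23% |

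**Step 4: can other data correct it?** The 24-hour recalls (three in the baseline week and three in the final week) measure restaurant intake without relying on either phone. C.3.e makes their comparison with the photos exploratory, and they say nothing about the weeks between. They can reveal a capture difference but do not enter the primary model.

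**The case against.** The strongest reply is that much of this rests on silence. The Dyad Component paragraph lists new features and is not the trial's measurement procedure. C.3 presents the control app as a cut-down version of the full one, so intervention parents most naturally have SNAP as well. That stands: a reader might infer that intervention parents have no photo step, and the documents do not support this. Nor do they say that control parents are never asked for a photo. Their app detects venue entry, and the baseline instruction addresses users generally. What remains is that the question about buying for the adolescent is described for one arm only.

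A reader might also infer that parent-bought meals will be counted twice, and more often in the intervention arm because the adolescent is notified. This is weak. Apart from the baseline sentence, the photo instructions in C.3 and C.3.c go by who makes the purchase, which points to the parent's photo as the record. The notification invites a message and not a photo. The missing rule is a gap to close, not evidence of duplication.

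Finally, a reader might say that one meal a week can create or erase the target effect. The arithmetic is right (765/650 = 118%), but it needs a net imbalance averaging a whole meal per dyad per week, which is 40% of the 2.5 planning value. Nothing in the documents suggests an imbalance that large. Misses or duplicates that are equal in both arms create no false difference, although they add noise and can rescale a real one.

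**Conclusion.** The point holds as a risk of unequal ascertainment of the primary outcome. Parent purchases are in the endpoint, the parent apps prompt differently by arm from week 3, and neither the baseline period nor the recalls correct this in the primary analysis. Photo capture by intervention parents is probable but unstated, and the one-meal-once rule is absent.

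Neither the size nor the direction of any bias can be established from the documents. Under the assumed range of 0.10 to 0.50 meals per week, the contrast moves by 12% to 59% of the target, and about 0.85 meals per week would be needed to equal it. These figures assume 765 kcal per parent-bought meal, and the error rates also assume the plan's SD and 60 analysed per arm. The pre-purchase question and suggestion are legitimate treatment. The objection is only that they also act as an unmatched prompt on the measurement. Because a cheap design change removes most of the difference, this deserves more than a wording clarification.

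**What to change.** 1. **Same request in both arms, from day 1 to the end.** After a detected restaurant visit, on exit or once the dwell time has passed, ask every parent neutrally whether they bought food for the adolescent and, if so, request a SNAP photo. The request must follow the purchase; on entry the answer is not yet known. The intervention's own question and suggestion stay as treatment on top of this. State explicitly that parents in both arms have SNAP.
2. **Counting rule.** State that the purchaser's photo is the record and that each meal counts once per dyad. Flag likely duplicates by venue and time for manual review and do not merge them automatically: takeaway food may be photographed later at home, and separate items may come from one venue. C.3.d does not list photo time and location among the data collected, so confirm that the app stores them.
3. **Reporting.** Report parent-sourced and adolescent-sourced calories separately by arm, and compare photo capture with the 24-hour recalls by arm in the baseline and final weeks.

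The cost is one extra neutral prompt per visit for control parents, a small app configuration change and some data cleaning. The treatment itself and the sample size do not change.

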### Automate Use of Restaurant Menus

In a project for Drexel University we added the ability for PiLR EMA to scan bar codes on food labels and search USDA and the private Nutritionix databases to return calorie and nutrient content to a personalized algorithm. Nutritionix is a commercially available food data base. On 12/13/2016, their web site contained 112,441 items from 664 restaurant brands. Our application program interface (API) to the Nutritionix database is a live connection that allows us to query in real time or batch download identifiers and nutritional information about menu items. For this project we will build an easily accessed means for dieticians to associate food preferences and recommendations with menus at registered venues.

**Development of Engagement Features** – The following new features will be developed into the program:

**Goal setting** Adolescents will indicate the goals they would like to set such as number of times per week to eat in a fast food venue, health rating of the foods they will consume (i.e. 50% of their choices each week will have a healthy or very healthy rating), number of meal photos they want to submit each week, etc. They will be able to share their goals with their parents (and friends if they have agreed to include a friend in the program). They

will also negotiate with their parents to establish a fitting reward for meeting their goals (i.e., they will enter their desired reward and parents will indicate agreement or propose revisions until they get to consensus).

**Point system** Adolescents will get points when they interact with the app (e.g., if they submit a photo of their meal, rate their meal (with extra points if it is rated as healthy or very healthy), and if they reach their goal); with bonus points if their parents make healthy choices. The system will pop up on their phone periodically to remind them of their score and how to earn more points. Design iterations will be informed by participants.

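### Primary calories come only from submitted photos, and no rule covers a detected visit without one, so a treatment-induced difference in photo-taking can be read as a difference in calories purchased

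*Combined protocol and SAP*

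**What the plan says.** **Outcome source.** C.3 (Primary Outcome) builds calories from photos: "the number of calories purchased will be calculated based on the photos submitted and the calorie content" that the restaurant publishes. C.3.e repeats it: "Calories purchased (by and for adolescents) will be assessed using annotated photos, and nutrition data from restaurant menus". C.3.e then fits a linear GEE on time, arm and their interaction. It does not state the outcome unit, the coding of time, or the handling of a visit or week without a photo. The unit kcal/week appears only in the power paragraph.

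**What differs between arms.** Both arms have location detection and photo submission. After a two-week run-in, the other features are switched on for the intervention arm in week 3 (C.3.c). In C.1 (Development of Engagement Features) points are earned, for example, "if they submit a photo of their meal, rate their meal (with extra points if it is rated as healthy or very healthy", and one possible personal goal is the "number of meal photos they want to submit each week". These are examples of a design not yet fixed: "Design iterations will be informed by participants". Of the control app, C.3 says: "It will not allow goal setting or assign points". Participants know their arm, because the technology team "will send a message to their phone indicating their group assignment" (C.3.b, Randomization).

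**Existing checks.** Visits are counted automatically (Secondary Outcome A), and C.3.d collects how often photos are submitted. C.3 adds that "24-hour food recalls will be conducted in the baseline week and final week (3 per week) to provide a comparison assessment" of restaurant calories. C.3.d treats the recalls as the reference measure, but C.3.e analyses them as exploratory.

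**The concern.** A purchase enters the primary outcome only if someone photographs it. Measured calories are thus roughly true purchases multiplied by the share photographed, and the intervention contains features that may move that share. Randomisation does not protect against this, because the features are part of the assigned treatment. The run-in shows capture before activation, not after it.

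The direction is open. Points for photos and a photo-count goal could raise intervention capture and hide a benefit. Extra points for meals rated healthy could favour photographing those meals and leaving out others, which would exaggerate a benefit. Without capture by arm and a stated rule for visits without a photo, neither a positive nor a null primary result can be separated from a change in photo-taking.

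**Working it through.** **Inputs from the documents.** 765 kcal per meal away from home, 2.5 such meals per week, target difference 650 kcal/week, SD 1200 kcal, 60 per group, two-sided alpha 0.05 (all C.3.e, Power); entry requires restaurant food at least 3 times per week (C.3.a).

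**Assumptions, not in the documents.** Capture rates; a weekly total as outcome; no photo counted as 0 kcal; omission unrelated to meal size.

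**1. The plan's own figure.** Standard error = 1200 × √(2/60) = 219.1. A t-test with 60 per group has 83.7% power for 650; 80% needs 55 per group. The stated 80% is slightly conservative. 60/(1 − 0.20) = 75 agrees. This does not bear on the point.

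**2. Shift from a capture gap.** Weekly calories = 765 × 2.5 = 1,912.5. A 10-point gap gives 0.10 × 1,912.5 = 191 kcal/week, and 191/650 = 29%. At 3 meals per week: 765 × 3 = 2,295; 0.10 × 2,295 = 230, and 230/650 = 35%. The gap that equals the whole target is 650/1,912.5 = 34 points, or 650/2,295 = 28 points.

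**3. No true effect, simple t-test, 10-point gap (2.5 meals per week).** Noncentrality = 191.25/219.1 = 0.87. The test rejects 13.9% of the time. If intervention capture is the higher one, 13.7% favour control and 0.2% favour intervention; if it is the lower one, these swap. If the SD falls with capture (70% control, 80% intervention), total rejection is 21.0% with SD proportional to capture (840/960) and 17.0% with random omission of 765-kcal meals (1006/1075).

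**4. True reduction of 650.**
- 70% control, 80% intervention: 0.70 × 1,912.5 − 0.80 × 1,262.5 = 1,338.75 − 1,010 = 329 kcal/week.
- 70% in both arms: 0.70 × 650 = 455 kcal/week.

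| SD assumption | Power, 70%/80% (329) | Power, 70%/70% (455) |
|---|---|---|
| Held at 1200 | 32% | 54% |
| Random omission | 40% | 69% |
| Proportional to capture | 51% | 84% |

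**5. The planned model.** Its time coding is not stated, so this is also an illustration: 12 weekly points, equal capture in weeks 1–2, a 10-point gap from week 3, SD 1200, exchangeable within-person correlation 0 to 0.5, no true effect.
- Linear time: a step at week 3 loads on the slope at 0.0699, so 0.0699 × 191.25 = 13.4 kcal/week per week. Standard error 18.3 to 13.0; rejection 11% to 18%.
- Run-in versus follow-up: shift 191.25, standard error 169.7 to 120.0; rejection 20% to 36%.

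A true 650 step loads on the slope at 0.0699 × 650 = 45.5, and 13.4/45.5 = 29%. The gap is therefore the same share of the target under either coding. As in step 3, nearly all rejections lie in the direction of the gap.

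**6. Other unit.** If the outcome were mean kcal per photographed purchase, omission unrelated to content would cancel. Only content-selective omission would bias the result.

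**The case against.** The strongest reply is that much of this is already handled. Both arms have the same photo tool and team contact, photo frequency and visits are recorded, and the recalls are planned in advance as a comparison with the photo method. That stands in part: a check exists. However, weekly contact is to see that the app works, the extent of app use is an exploratory covariate that treatment can itself change, the recalls are exploratory, and no report of capture by arm is tied to the primary result. The three-week non-use rule in C.3.d triggers an early interview; it is not an analysis rule.

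A second reply is that a week without photos can be a true zero. This stands. Fewer visits are an intended effect, and C.3.d expects some participants to stop visiting restaurants. A visit without a purchase can be intended too: in C.1 (Dyad Component) the adolescent may tell a parent that no food is needed. Any rule must keep genuine zeros.

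Third, the size rests on assumptions. This also stands. The 90.2% reported from the Phase 1 pilot is response to notifications, not photo capture.

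A reader might infer from the rejection rates that the trial has an 11% to 36% risk of a false claim of benefit. The documents do not support that. If photo rewards raise intervention capture, such a claim becomes rarer than the nominal 2.5%.

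**Conclusion.** The concern holds and should be fixed. The omission is certain: primary calories depend on photos, the intervention alone adds features that may affect photo-taking, and nothing states what a detected visit without a photo contributes. The size of any bias is not known. Under a weekly total with missing photos at zero, 10 points of unequal capture is worth 191 kcal/week, 29% of the target, towards masking if the intervention arm photographs more and towards a false or enlarged benefit if it photographs less.

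Two stronger readings should be resisted. One is that the point system will bias the result in a known direction; its design was still open and its examples pull both ways. The other is that the photo outcome is unusable and the recalls should replace it; the recalls cover six self-reported days from participants who know their arm, so they can support the primary result but not overrule it.

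**What to change.** 1. **Outcome definition.** State kcal/week as the GEE outcome and state how time is coded. Separate three cases: no detected visit while the app is working (zero); a detected visit without a photo (purchase unknown, not zero by default); and a week when the app is not running (missing).
2. **Capture by arm.** Report photos per detected visit by arm, for run-in and follow-up, beside the primary result. Show user-registered venues and parent-app visits separately where the app data allow. Registering a venue is an active step that points could encourage, and it can raise later passive detections at that venue, so say that this denominator is imperfect.
3. **Recalls.** Report the planned arm contrast in restaurant kcal from the 24-hour recalls beside the primary result, as a prespecified supportive analysis with no veto.
4. **Sensitivity analysis.** For detected visits without a photo, vary the assumed non-purchase share and an arm-specific delta over a stated range, and report where the conclusion changes.

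The cost is analysis work. Visits, photos and recalls are already to be collected, but the documents do not say that non-purchase will be recorded, so item 4 depends on assumed shares and will give wider, assumption-driven results.
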